## 4. STUDY ENROLLMENT AND WITHDRAWAL

### 4.1 PARTICIPANT INCLUSION CRITERIA

To be eligible to participate in this study, an individual must meet all of the following criteria:

1. Ability to understand and the willingness to sign a written informed consent document.
2. Age  $\geq 18$  years at time of informed consent. All people regardless of biologic sex and members of all races and ethnic groups will be included.
3. Must be listed or recommended to be listed for orthotopic liver transplantation at the participating institution
4. Have a CP score  $\geq B8$ , as defined in Appendix A
5. Eastern Clinical Oncology Group (ECOG) performance status  $\leq 2$ , or Karnofsky Performance Scale  $>60$  (refer to Appendix B)
6. Must have a life expectancy  $> 12$  weeks
7. Safe radiation treatment planning parameters that adhere to all organs at risk constraints per section 5.1 of the protocol. If normal organs at risk constraints (including at least 700cc of uninvolved liver) are unable to be met at the lowest dose modification (30 Gy in 5 fractions), the patient is deemed ineligible for SBRT and deemed a screen failure.
8. Except for prior radiotherapy or radioembolization, other prior therapies to previously treated lesions, are permitted.
9. People of childbearing potential must have a negative urine or serum pregnancy test within 72 hours prior to receiving the first dose of SBRT. If the urine test is positive or cannot be confirmed as negative, a serum pregnancy test will be required.

Participants of childbearing potential are those who have not been surgically sterilized or have not been free from menses for  $>1$  year without an alternative medical cause.

*Note: Abstinence is acceptable if this is the preferred contraception for the participant.*

10. No other prior invasive malignancy is allowed except for the following: adequately treated basal (or squamous cell) skin cancer, in situ breast or cervical cancer. Stage I or II invasive cancer treated with a curative intent without evidence of disease recurrence for at least five years.

### 4.2 PARTICIPANT EXCLUSION CRITERIA

An individual who meets any of the following criteria will be excluded from participation in this study:

1. Participants have any one of the following liver tumor characteristics:
  - a. have  $> 5$  liver tumors, or
  - b. maximal diameter  $> 5$  cm
2. Complete obstruction of portal venous flow to the segment of liver that includes the target lesion
3. Prior radiotherapy to the upper abdomen or radioembolization of the liver, or prior thermal

ablation to the target lesion.

4. For fiducial marker placement:
  - a. Have a gold allergy,
  - b. Any coagulopathy preventing safe fiducial placement
5. Contraindication to both contrast enhanced MRI and contrast enhanced CT (i.e. unable to undergo follow-up imaging or SBRT treatment planning)
6. Participation in another concurrent treatment protocol
7. Participant is pregnant or breastfeeding, or expecting to conceive or father children within the projected duration of the trial, starting with the screening visit through 120 days after the last dose of trial treatment.
8. Uncontrolled intercurrent illness, including but not limited to, ongoing or active infection, symptomatic congestive heart failure, uncontrolled hypertension, unstable angina pectoris, cardiac arrhythmia, interstitial lung disease, serious chronic gastrointestinal conditions associated with diarrhea, or psychiatric illness/social situations that would limit compliance with study requirement, substantially increase risk of incurring AEs or compromise the ability of the patient to give written informed consent

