### 3. STUDY DESIGN AND ENDPOINTS

#### 3.1 DESCRIPTION OF THE STUDY DESIGN

*Refer to Section 9, Statistical Considerations, for additional information regarding statistical methods used in this study.*

This is pilot study to assess the feasibility of bridge-to-transplantation SBRT for patients with severe liver disease. Participants must meet the inclusion criteria, have none of the exclusion criteria, and have provided written informed consent before the conduct of any screening tests not performed routinely in their treatment.

In general, patients with CP-B8 or higher cirrhosis and non-metastatic HCC who have been listed or recommended to be listed for liver transplantation will be eligible for participation in this study. Eligible participants will undergo SBRT consisting of 40 Gy to be given in 5 fractions every other day provided that criteria for normal organ constraints are met (i.e.,  $\geq 700$  cc of uninvolved liver). In cases where normal organ constraints are not met, the dose will be iteratively de-escalated to two dose levels (35 Gy in 5 fractions, then 30 Gy in 5 fractions). If normal organ constraints are unable to be met at 30 Gy in 5 fractions, the participant will be considered ineligible for SBRT and considered a screen failure.

Following SBRT, the rate of radiation-induced liver disease (non-classical RILD) and associated toxicities will be evaluated, along with treatment response and an assessment of quality of life associated with SBRT. The proportion of participants that are successfully bridged to liver transplantation, and times to liver transplantation following SBRT will be recorded for each participant. Additional exploratory studies will assess SBRT-related histopathologic changes in explanted livers of participants with advanced cirrhosis. In these studies, pathologic treatment response in explanted livers will be evaluated, and regions of uninvolved liver both near and remote to the irradiated volume will be assessed for histopathologic changes consistent with RILD (e.g., obliteration of central veins, increased perisinusoidal reticulin network and hepatocyte necrosis).

This study aims to enroll 15 participants at OHSU. Participant data for primary, secondary, and exploratory endpoints will be collected by the site providing clinical care. The analyses of the data collected will take place at OHSU.

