#### 3.2 STUDY ENDPOINTS

##### 3.2.1 PRIMARY ENDPOINT

Endpoint	Start	End
Proportion of participants who are transplanted or with localized disease control that meets Milan criteria (Section 7.5) within 1 year	Start of SBRT	Time of progression, or transplantation, or 1-years after last SBRT dose, whichever occurs first

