## 7.5 MILAN CRITERIA

Participant eligibility for transplantation will be based on guidelines reported by Mazzaferro et al. To be considered eligible for liver transplantation, participants with HCC must have disease as follows:

- Single tumor with diameter  $\leq 5$  cm **OR** up to 3 tumors, each with diameter  $\leq 3$  cm, **AND**
- No major vessel or extra-hepatic involvement.

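### Entry limits are wider than the Milan criteria that define primary success, and baseline Milan status is not used, so one proportion can mix bridging with down-staging

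*Combined protocol and SAP*

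**What the plan says.** **Entry.** Exclusion 1 in section 4.2 opens with "Participants have any one of the following liver tumor characteristics" and gives two limits: "have $> 5$ liver tumors, or" and "maximal diameter $> 5$ cm". Between 1 and 5 tumors are therefore admitted, each up to 5 cm whatever their number. The vascular exclusion is "Complete obstruction of portal venous flow to the segment of liver that includes the target lesion". Inclusion 3 in section 4.1 reads "Must be listed or recommended to be listed for orthotopic liver transplantation at the participating institution" and does not refer to section 7.5. Section 3.1 describes the population as having "non-metastatic HCC who have been listed or recommended to be listed for liver transplantation".

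**Endpoint.** Section 3.2.1 defines the primary endpoint as "Proportion of participants who are transplanted or with localized disease control that meets Milan criteria (Section 7.5) within 1 year". Section 7.5 requires a single tumor of 5 cm or less, or no more than 3 tumors of 3 cm or less each, and adds "No major vessel or extra-hepatic involvement".

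**Analysis.** Section 9.2.2 reports one proportion with an exact 95% CI in the efficacy set. Section 9.1 defines that set by receipt of 85% or more of the prescribed dose. Neither section uses baseline Milan status.

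**Purpose.** Sections 1.3 and 3.1 describe a bridging study, and 1.3 says the pilot should help to estimate bridging efficacy against historical controls. Section 1.1 gives the only background rate: 20-30% of listed patients progress beyond Milan while waiting.

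**The concern.** Bridging means that a candidate stays transplantable until an organ is available. That can be observed only in someone who is within Milan at the start. For someone who starts outside, reaching Milan requires shrinkage, which is a different effect with a different expected rate.

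The plan scores both kinds of participant with one rule. Take a participant who enters with 4 tumors, has stable disease and is not transplanted within the window. That participant fails, although the treated disease never progressed. A participant who enters with 4 tumors and shrinks into Milan succeeds, but through down-staging, which the protocol does not mention.

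The reported proportion then depends partly on how many entrants started outside Milan. It is also not like for like with the 20-30% in section 1.1, which describes loss from within Milan. A later, larger trial planned from this number could take it for a bridging rate when it is a blend.

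**Working it through.** **1. The plan's own figure.** Section 9.3.1 justifies n = 15 by the chance of meeting at least one SBRT-ineligible patient when the probability is 20%. n = ln(1 − 0.95)/ln(1 − 0.20) = 13.43, rounded up to 14; at n = 15 the chance is 1 − 0.80^15 = 96.5%. The stated 15 is consistent with this. It does not involve the Milan criteria, so nothing below changes it.

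**2. Entry limits against section 7.5.** Cross tumor number (1 to 5) with largest diameter (up to 3 cm, or above 3 and up to 5 cm).

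| Tumors | Largest up to 3 cm | Largest above 3, up to 5 cm |
|---|---|---|
| 1 | within Milan | within Milan |
| 2 | within | outside |
| 3 | within | outside |
| 4 | outside | outside |
| 5 | outside | outside |

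All 10 classes pass section 4.2; 4 are within Milan and 6 are outside. These are classes, not patient frequencies. The vascular rules differ too: 4.2 bars only complete portal obstruction to the target segment, while 7.5 bars any major vessel involvement.

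**3. Chance that the issue arises.** The share q of participants outside Milan at entry is not in the documents, so a range is assumed. The chance of at least one among 15 is 1 − (1 − q)^15:

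- q = 5%: 54%, expected number 0.75
- q = 10%: 79%, expected number 1.5
- q = 20%: 96%, expected number 3

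**4. Ceiling on the primary proportion.** Suppose all 15 are analysed, k start outside Milan and are neither transplanted nor down-staged, and everyone else succeeds. The ceiling is (15 − k)/15, shown with Clopper-Pearson limits.

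| k | Ceiling | Exact 95% CI |
|---|---|---|
| 0 | 15/15 = 100% | 78.2-100 |
| 1 | 14/15 = 93.3% | 68.1-99.8 |
| 2 | 13/15 = 86.7% | 59.5-98.3 |
| 3 | 12/15 = 80.0% | 51.9-95.7 |
| 4 | 11/15 = 73.3% | 44.9-92.2 |
| 5 | 10/15 = 66.7% | 38.4-88.2 |

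**5. Dependence on case mix.** Assume 75% success within Milan, the midpoint of the 70-80% left after the 20-30% loss in section 1.1, and let a fraction s of the outside group be down-staged or transplanted. The expected proportion is 0.75(1 − q) + s·q.

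- s = 0: 67.5% (q = 10%), 60% (q = 20%), 52.5% (q = 30%)
- s = 0.5: 72.5%, 70%, 67.5%

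The bridging rate is 75% in all six cases, yet the reported figure runs from 52.5% to 72.5%.

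**The case against.** The best reply is that listing already acts as a Milan filter. Inclusion 3 requires listing or a recommendation to list; section 7.5 makes Milan disease a condition of transplant eligibility; and section 1.1 speaks of listed patients progressing beyond Milan, which implies that they begin inside it. This has force: such entrants may be few, or there may be none. But inclusion 3 does not invoke 7.5, a recommendation to list is enough, and section 1.1 calls transplant eligibility largely, not wholly, Milan-based. One might argue in return that the wider limits in 4.2 would be pointless if Milan were already required. That is only an inference, because overlapping criteria are common and do not show that outside-Milan entrants are expected.

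A second reply is that the scoring follows the endpoint. Section 2.1 speaks of control sufficient for transplant eligibility criteria, not of preserving eligibility already held. A participant who is outside Milan and untransplanted at 1 year is not eligible under 7.5, so counting a failure is not misclassification. This stands. What remains is a question of interpretation: the study is described as bridging, but the number need not measure bridging alone.

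A reader might also infer three stronger things that the documents do not support:

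- **Every outside-Milan entrant costs 1/15 = 6.7 points even with perfect control.** Not so. Under 3.2.1 transplantation is a success, and so is control with shrinkage into Milan. Sections 7.1.1 and 7.3.1 measure viable tumor, and 7.5 does not say whether its diameters are viable or total, so a complete response might also qualify.
- **Extrahepatic disease is admitted at entry.** It is not named in 4.1 or 4.2, but section 3.1 restricts the study, in general terms, to non-metastatic disease.
- **Even flawless SBRT would look no better than background.** That needs k of 3 or more with nobody transplanted or down-staged. The section 1.1 figure concerns listed patients over an unspecified wait, not Child-Pugh B8 or higher at 1 year, and section 9 plans no comparison or threshold.

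**Conclusion.** The point holds as a gap between entry limits and endpoint that affects interpretation. Section 4.2 admits tumor patterns outside section 7.5, no entry criterion requires baseline Milan status, and section 9.2.2 does not use it. The one reported proportion can therefore combine Milan maintained with Milan attained.

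The size depends on a number the documents do not give. With none of 15 outside Milan there is no effect. With 1, 2, 3 or 5 outside, and none of them transplanted or down-staged, the ceiling is 93.3%, 86.7%, 80.0% or 66.7%. These figures assume that all 15 are analysed; the 85% dose rule could make the denominator smaller and each participant's weight larger. No particular k is supported by the text.

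This does not invalidate the pilot, its sample size or its descriptive aim. It is a cheap improvement to what the main result can say about bridging.

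**What to change.** Reconcile sections 4.1 and 4.2 with 7.5 and 9.2.2, so that the plan says whether participants outside Milan at entry are intended. Which entry limit to use is a clinical and accrual decision and is not proposed here.

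Whatever is decided, add to section 9.2.2:

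1. Baseline Milan status is derived for each participant from the screening imaging already required in sections 6.8 and 7.2.
2. The overall primary proportion is kept as planned.
3. The primary endpoint is also reported, with exact 95% CI, for participants within Milan at baseline (maintained or transplanted) and for those outside (attained or transplanted).

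The cost is one derived field and one table split, with no new procedure and no change to n = 15. The intervals widen. For example, with 12 within and 3 outside (assumed), 12/12 has a lower limit of 0.025^(1/12) = 73.5%, against 0.025^(1/15) = 78.2% for 15/15; 0/3 has an upper limit of 1 − 0.025^(1/3) = 70.8%. The outside group would be little more than a listing, which is adequate for a descriptive pilot.

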#### **4.3 STRATEGIES FOR RECRUITMENT AND RETENTION**

Participants for this study will primarily be recruited from hematology and oncology practices within OHSU and its affiliated community hematology and oncology (CHO) practices. Participants may also be identified and referred to this study by their primary treating physician from within OHSU, CHO, VAPORHCS, or from the outside community. Participants may be identified by a member of the patient's treatment team, the PI, research team, or medical and surgical oncology clinics part of OHSU, CHO, or VAPORHCS. As a member of the treatment team, the investigator(s) will screen their patient's medical records for suitable research study participants and discuss the study and their potential for enrolling in the research study, which may include discussion of patient at a multidisciplinary liver tumor board meeting. In these meetings, a participant's medical history will be presented at a multidisciplinary comprised of hepatobiliary surgical oncologists, medical oncologists, radiologist, radiation oncologists, and hepatologists. In this conference, patient imaging and pathology may be reviewed by the group for consensus that the prospective participant satisfies all inclusion and exclusion criteria. Referral of potential participants to investigator(s) of this study is made as part of standard of care, with the referring physician seeking advice on the diagnosis, evaluation, and/or treatment of the patient's malignancy.

The investigator(s) may also screen the medical records of potential participants with whom the investigator does not have a treatment relationship. This will be done for the limited purpose of identifying patients who would be eligible to enroll in the study and to record appropriate contact information in order to approach these potential individuals regarding the possibility of participating in the study. Participants may also initiate contact with the investigator through information of this study posted on the [clinicaltrials.gov](https://clinicaltrials.gov) website.

##### **4.3.1 ACCRUAL ESTIMATES**

The number of participants to be accrued is driven by the study primary objective. An estimated 15 participants over a 12 month period.

This study will not focus on any particular gender, racial or ethnic subset. No participant will be excluded from the study on the basis of gender, racial or ethnic origin. Gender-nonconforming and gender-fluid individuals as members of the general population will also be recruited. Male, female and minority volunteers will be recruited for this study from the general population. The incidence of male HCC is disproportionately higher than females; at a rate of approximately 2:1 across studies reported. The projected gender, racial, and ethnic composition of the study, adjusted for the approximate 2:1 disproportion in male to females, will otherwise represent that of the state of Oregon (**Table 1**).

**Table 1. Projected accrual for present study based on Oregon population demographics**

Ethnic Category [OR]	Sex/Gender					
	Females		Males		Total	
	n	%	n	%	n	%
Hispanic or Latino	0-1	6.5	1-2	6.3	2	12.8
Not Hispanic or Latino	3	44.0	9	43.2	12	87.2
Ethnic Category: Total of all participants*	4		11		15	100*
Racial Category						
American Indian or Alaskan Native	0	0.9	0	0.9	0	1.8
Asian	0	2.3	0-1	2.2	1	4.5
Black or African American	0	1.1	0	1.0	0	2.1
Native Hawaiian or other Pacific Islander	0	0.2	0	0.2	0	0.4
White	3	44.1	9	43.3	12	87.4
Two or more races	0	1.9	0-1	1.9	1	3.8
Racial Category: Total of all participants*	4	50.5	11	49.5	15	100
Source:	Adapted from U.S. Census Bureau, 2017.					
*Totals may not equal 100 due to rounding.						

#### 4.3.2 INCLUSION OF CHILDREN

This protocol does not include children as the number of children with this type of cancer is limited.

### 4.4 REGISTRATION PROCEDURES

There is no randomization for treatment in this study. Participants will be required to give written informed consent to participate in the study before any screening tests or evaluations are conducted that are not part of standard care.

#### 4.4.1 OHSU REGISTRATION

Registration from all consented participants must be entered into the OHSU electronic Clinical Research Management System (CRMS, e.g., eCRIS). The OHSU coordinating center team will verify completeness of documents, enter registration information into the CRMS, and assign a study number/identifier. At a minimum, registration of OHSU participants will include signed copies of the most recently IRB-approved, informed consent form and HIPAA authorization.

## 4.5 PARTICIPANT SCREENING AND ENROLLMENT

In order to participate in this study, signed informed consent must be obtained from the participant or the participant's legally acceptable representative. The current Institutional Review Board (IRB) approved informed consent must be signed and dated by each participant prior to undergoing any study procedures or before any prohibited medications are withheld from the participant in order to participate in this study.

Screening will begin once the participant has provided written informed consent to participate in the study and ends on Day 1 of the study. All screening and baseline evaluations will be performed during the screening phase (i.e., up to 28 days before on-study treatment is initiated). Day 1 of the clinical trial will be when participants are administered first dose of SBRT. Total accrual of all participants is anticipated to take a total of 12 month.

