Secondary Endpoints	
 
1. Incidence of progressive disease within or at the planned tumor volume (PTV) margin (i.e. local control)
 
2. Incidence of progressive disease within any section of the liver, including the PTV (e.g. intrahepatic disease free survival)
 
3. Incidence of progressive disease outside of the liver (e.g. extrahepatic disease free survival)
 
4. Overall Survival
 
5. Proportion of participants that proceed to transplantation
 
6. Incidence of non-classical radiation-induced liver disease (RILD), defined as grade 4 aspartate aminotransferase or alanine aminotransferase elevation, or an increase in CP score of <math>\geq 2</math> within 1 week to 3 months after completing SBRT.
 

	7. Incidence of liver toxicity per CTCAE v5.0 within 1 week to 3 months after completing SBRT.
Exploratory Endpoints	
 
1. QoL scores for EORTC QLQ-C30 questionnaire
 
2. QoL scores for Functional Assessment of Cancer Therapy-Hepatobiliary (FACT-Hep) questionnaire
 
3. At time of transplantation, histopathologic changes in irradiated tumor sites relative to uninvolved liver tissue will be assessed
 

Number of Participants	15
Duration of Therapy	SBRT will be administered as 5 fractions every other day (~10 day)
Duration of Follow Up	Time of progression, or transplantation, or 2-years after last SBRT dose, whichever occurs first
Key Inclusion Criteria	
 
1. Participants aged <math>\geq 18</math> years
 
2. Patient diagnosed with HCC and recommended for LTX
 
3. Meets clinical criteria for eligibility for SBRT to the target lesion
 
4. Childs-Pugh Class B8 or higher
 
5. Eastern Clinical Oncology Group performance status <math>\leq 2</math>
 
6. Safe radiation treatment planning parameters that adhere to all organs at risk constraints per section 5.1 of the protocol. If normal organs at risk constraints (including at least 700cc of uninvolved liver) are unable to be met at the lowest dose modification (30 Gy in 5 fractions), the patient is deemed ineligible for SBRT and deemed a screen failure.
 

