##### 6.1.4.1 Vital signs

Vitals to be collected include BP, HR, temperature, and oxygen saturation by pulse oximetry. As part of screening/baseline visit, vitals should be obtained within 14 days prior to first dose of SBRT. Vitals will also be obtained during treatment.

Significant findings that were present prior to the signing of the informed consent must be included in the Medical History CRF. Significant new findings that begin or worsen after informed consent must be recorded on the Adverse Event CRF.

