#### 6.1.6 ADVERSE EVENT EVALUATION

Toxicities and adverse experiences will be assessed at each visit using the [CTCAE v5.0](#) and quantifying current Child-Pugh score to assess risk of RILD. Adverse events will be monitored from the time the participant signs the Consent Form up until 3 months following SBRT. Participants will be instructed to report all AEs during the study and will be assessed for the occurrence of AEs up until 3 months following radiation therapy. All AEs (serious and non-serious) must be recorded on the source documents and CRFs regardless of the assumption of a causal relationship with the study therapy.

For details on AE collection and reporting, refer to Section 8.6.

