##### 6.1.6.1 Radiation-induced liver toxicity

Radiation-induced liver disease (RILD) is defined as either classical or non-classical RILD. Classical RILD (typically occurring in patients without background liver dysfunction or cirrhosis) is characterized as the presence of nonmalignant ascites and anicteric elevation of alkaline phosphatase level twice the upper level of normal or baseline value occurring between 2 weeks and 3 months after the completion of irradiation. Non-classical RILD (typically occurring in patients with baseline liver dysfunction or cirrhosis), occurs is defined as grade 4 AST and/or ALT elevations, or an increase in CP score of  $\geq 2$  within 1 week to 3 months after completing SBRT.

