## 6.3 SCREENING ASSESSMENTS

A screening (consultation) visit may occur as part of standard of care. If a participant is eligible for the study after review of key inclusion/exclusion criteria, additional screening visits will be scheduled while staff members are requesting insurance authorization to participate in a clinical trial.

The following will be reviewed at screening visit:

- Clinical history and physical exam (per standard of care)
- Informed consent obtained and documented

Toxicities which occur prior to the start of treatment will not be subject to analysis. Consent must be obtained before initiation of any clinical screening procedure that is performed solely for the purpose of determining eligibility for this research study. Evaluations performed as part of routine care before informed consent can be utilized as screening evaluations if done within the defined time period.

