### 9.1 ANALYSIS POPULATIONS

Safety analysis set: All participants will be evaluable for toxicity from the time of their first fraction of SBRT.

Efficacy analysis set: The analysis population to assess transplantation eligibility (i.e., Milan criteria) and efficacy endpoints (e.g., localized control rate, intrahepatic progression, extrahepatic progression and overall survival), will include only participants who have received at least 85% of the prescribed SBRT dose (i.e., 85% Level 0 = 34 Gy; 85% Level -1 = 30 Gy; 85% Level -2 = 25.5 Gy).

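### The Child-Pugh rise that defines RILD has no named reference reading, and the only scheduled pre-SBRT bloods may be 28 days old and also decide entry

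*Combined protocol and SAP*

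**What the plan says.** - **Endpoint.** Section 6.1.6.1 defines non-classical RILD as "grade 4 AST and/or ALT elevations, or an increase in CP score of" 2 or more, "within 1 week to 3 months after completing SBRT". Section 3.2.2 uses the same definition. Section 9.2.3 also reports the Child-Pugh rise by itself, as a proportion with an exact confidence interval in the safety set. None of these sections, nor footnote H to the schedule in 6.8, says which reading the rise is counted from.
- **Age of baseline.** Section 4.5: "All screening and baseline evaluations will be performed during the screening phase (i.e., up to 28 days before on-study treatment is initiated". The screening column in 6.8 runs from Day -28 to Day -1.
- **Bloods.** Section 6.8 marks biochemistry and coagulation at screening and follow-up, and on none of the five treatment days. Section 6.2.3 gives the Child-Pugh score as the reason for collecting INR.
- **Score at visits.** Section 6.1.6 asks at each visit for CTCAE grading and for "quantifying current Child-Pugh score to assess risk of RILD". Section 6.8 marks an adverse event assessment on Day 1.
- **Entry.** The Synopsis requires "Childs-Pugh Class B8 or higher"; section 4.1 has the same threshold.
- **Start of toxicity.** Section 6.3: "Toxicities which occur prior to the start of treatment will not be subject to analysis". Section 9.1: "All participants will be evaluable for toxicity from the time of their first fraction of SBRT".
- **Albumin.** It is one of the five components in Appendix A and is listed in 6.2.2, but footnote G to the schedule leaves it out of the liver panel.

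**The concern.** A change endpoint needs a defined starting value. Here the only starting value that the schedule can supply is the screening score, which creates two problems.

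First, that score can be four weeks old in patients with advanced cirrhosis, whose liver function may fall without treatment. A fall before fraction 1 that persists to the first follow-up draw at 6 weeks would look like RILD.

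Second, the patient was admitted because that reading was 8 or more. Some readings reach 8 by chance, and those patients tend to read lower next time. Change from the selecting reading is therefore biased downward, and some true rises of 2 will not reach the threshold.

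With one arm, no control group shares these errors and lets them be seen. Section 8.4.1 cites non-classical RILD rates of 20–30%, which is 3.0–4.5 of 15 patients, so one misclassified patient moves the rate by 1/15 = 6.7 points. Vital signs, by comparison, have a tighter limit in 6.1.4.1: "vitals should be obtained within 14 days prior to first dose of SBRT". That is a contrast in care over timing and not an error in itself.

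**Working it through.** The plan gives no figure for this point, so there is none to reproduce. The check has a textual part and two illustrations on assumed inputs.

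**1. Which reading can serve as the reference?** Section 6.1.6 wants a current score at each visit, and Day 1 has an adverse event assessment. But a score needs bilirubin, albumin and INR, and none is scheduled on Day 1. As scheduled, a rise can be computed only from the screening draw. Sections 6.3 and 9.1 mean toxicity to count from treatment start, but give no score at that time to which the rule could be applied.

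**2. Drift before fraction 1.** The documents give no rate of Child-Pugh rise without SBRT. Assume that a proportion *b* rise by 2 or more per 3 months (91 days), at constant hazard, and that the decline persists to follow-up. Then *h* = -ln(1 - *b*)/91, and the share falling in a gap of *d* days is 1 - exp(-*h d*).

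- *b* = 5%, *d* = 28: *h* = 0.0513/91 = 0.000564; 1 - exp(-0.0158) = 1.6%; × 15 = 0.23 patients.
- *b* = 10%: 3.2%, or 0.48 patients.
- *b* = 15%: 4.9%, or 0.73 patients.
- *b* = 20%: *h* = 0.2231/91 = 0.00245; 1 - exp(-0.0687) = 6.6%, or 1.0 patient.
- With *d* = 7 the range falls to 0.4–1.7%.

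**3. Selection on the same reading.** All inputs are assumed: true scores normal with mean 7, 8 or 9 and SD 1.5; within-patient SD 0.5, 0.75 or 1.0; readings rounded to whole points between 5 and 15; entry if the screening reading is 8 or more; 25% of patients truly rise by 2 and the rest do not change. The simulation used 1 million draws per setting. The observed rate is 0.75 × P(false rise) + 0.25 × P(true rise detected).

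- Smallest effect (mean 9, SD 0.5). From screening: 0.75 × 0.018 + 0.25 × 0.718 = 19.3%. From an independent pre-SBRT reading: 0.75 × 0.024 + 0.25 × 0.742 = 20.4%. Difference 1.1 points.
- Largest effect (mean 7, SD 1.0). From screening: 0.75 × 0.061 + 0.25 × 0.475 = 16.5%. Independent: 0.75 × 0.148 + 0.25 × 0.635 = 27.0%. Difference 10.5 points.

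Across the nine settings, a true rise is detected in 48–72% of cases from the screening reading and in 63–74% from an independent one. The gap in observed rates is not all missed rises: in the largest case, 0.25 × (0.635 - 0.475) = 4.0 points are missed rises and 0.75 × (0.148 - 0.061) = 6.5 points are fewer false ones. In all nine settings the independent reading gives the rate nearer to the true 25%.

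**4. Scale.** For 4 of 15 (26.7%), the exact 95% confidence interval is 7.8–55.1%.

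**The case against.** The strongest case against is that the plan never adopts the stale reading. That is right, and it limits the point in several ways.

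- A reader might infer that the screening score is the chosen reference. No section says so; 6.1.6 points instead towards a Day 1 score that the blood schedule cannot support. The defect is an undefined baseline and a conflict between sections.
- A reader might infer one reading only. Section 6.3 allows additional screening visits and 6.7 has unscheduled results recorded, so later bloods may exist. None is required.
- A reader might infer that routine-care results from before consent make the baseline older. Section 6.3 accepts them only within the defined period.
- A reader might take the 31% rate in 1.4.1 as a background hazard. It was observed within 6 months after SBRT and contains any treatment effect, so it cannot size decline before treatment.

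It can also be said that both biases rest on assumed inputs, that they oppose each other with unknown net sign, and that each is small beside the interval at 15 patients in a pilot without a formal test. All of this stands. But a wide interval does not correct a bias, and opposing errors of unknown size cannot be relied on to cancel. A score near fraction 1 also cannot be recovered after treatment has begun.

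**Conclusion.** The point holds as a gap in definition and scheduling. The Child-Pugh part of RILD lacks a named reference, and the only scheduled pre-SBRT bloods that could supply one may be 28 days old and also decide entry. As scheduled, pre-treatment decline can be counted as RILD, contrary to the intent of 6.3 and 9.1, and selection can hide true rises.

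The sizes are illustrations only. The upward effect of 1.6–6.6 points assumes that every patient has the full 28-day gap; the downward effect of 1–11 points depends on the assumed score distribution and variability. The documents settle neither size nor the net direction.

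Two stronger conclusions are not supported. The documents do not make counting pre-treatment decline a rule. Nor does this gap alone prevent the RILD rate from being read as an effect of SBRT: natural decline after SBRT remains in any single-arm design whatever the baseline, and 1.4.1 already concedes the difficulty. The grade 4 AST/ALT part of RILD is not a change in Child-Pugh score and is unaffected. The change is worth making because it is cheap and removes an avoidable source of error.

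**What to change.** - In 6.8, schedule all five Child-Pugh components (bilirubin, albumin, INR, ascites, encephalopathy) on Day 1 before fraction 1, or within 7 days before it, and record the date.
- In 3.2.2, 6.1.6.1 and 9.2.3, name that score as the reference for the rise of 2 or more. Keep the screening score for eligibility.
- Reconcile 6.1.6, 6.2.2 and 6.8, so that each visit at which a Child-Pugh score is expected has the bloods for it and footnote G includes albumin.
- As an optional check, report the change from the screening score as well.

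The cost is one routine blood draw at an existing visit and a few sentences. There is no extra draw if the screening draw is timed to the last 7 days before fraction 1; that reduces the drift but leaves the selection effect, because the same reading would still decide entry. The sample size does not change.
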